6.5 Overall experience / Route cause investigation (10 mins)

Now that you have performed the test I want to ask you about your experience of doing this.

Did you have any difficulties?
 Probe: Root cause and areas of difficulties observed

6.6 Knowledge based questions

I am now going to ask you some questions about using the COVID-19 testing kit.

This is not a memory test, and I would like you to refer to the instructions when answering these
questions.

Question number	Knowledge based question	Acceptance criteria
1	How often is it recommended that you do this test?	Depends on circumstances and current national or local guidelines
2	Where can you find information on what to do if you	NHS guidance online.
	have coronavirus symptoms or have a positive test for coronavirus?	nhs.uk/conditions/coronavirus- COVID-19
3	What are you advised to do if you have coronavirus symptoms and are deteriorating, or your symptoms last longer than a week?	User indicates one or all of following: Go online to: NHS 111 online
		coronavirus service, 111.nhs.uk .
		If you do not have internet access, call NHS 111.
		For a medical emergency dial 999.
4	What should you do if there is something missing or damaged in the kit?	User indicates one or all of the following:
		Do not use it.
		Call, using the numbers below, and ask for a new kit: - England, Wales and Northern Ireland: 119 (free from mobiles and landlines) - Scotland: [name] (charged at your standard network rate)
5	If while using the kit something breaks what in addition should you do?	Report the problem via the Coronavirus Yellow Card website, coronavirus- yellowcard.mhra.gov.uk
6	How should you ensure your hands are clean before you start using the test?	Wash your hands thoroughly for 20 seconds, using soap and warm water OR use hand sanitiser
7	Once you have opened the test kit when should the test be started	Within 30 minutes
8	What should you do if you touch the swab with your gum?	Get a new swab.
9	How long should you wait before reading the test result?	30 minutes.

10	What should you do if you leave the test to develop but get distracted and only come back to looking at the test after 1 hour?	If you leave the test to develop for longer than 35 minutes this will make the test result invalid.
11	What does this test result indicate:	Two lines – even faint lines – indicate the test is positive.
12	What does this test result indicate:	The test is invalid
13	What does this test result indicate:	This indicates the test is negative.
14	How should you report a positive result?	Answers can include: Report online www.gov.uk/covid19-self-test- help/ Or scan this QR code with your smart phone to open the reporting website Report by telephone England, Wales and Northern Ireland: 119 (free from mobiles and landlines) Scotland: [name] (charged at your standard network rate)

15	What should you do if a child's symptoms are worsening?	Visit NHS online www.111.nhs.uk or call 111
16	How should the test kit be disposed of after using?	Put all of the used test kit contents in the waste bag provided and place in your household waste

AFTER 30 MINUTES HAVE PASSED AND TIMER RINGS, PROCEED TO READ RESULTS

6.7 Reading the test results (5 mins)

We have now reached the time to read your test results. Can you now tell me what the result is?

Ask to describe what they see.

Participant answer:.....

Circle applicable

Correct interpretation: Success

Incorrect interpretation: Use error

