4.4 Simulated use adult and adolescents

Participants will be asked to open the pack and to follow the steps of use presented to them.

The moderator will observe the participant complete the steps of use. To ensure the task is representative of a real-use scenario, the moderator will not interact with the participant during this task and will not offer help to the participant. The moderator will only verbally interject if the participant gives up on the task, or if the moderator foresees a dangerous scenario developing. A list of tasks and their success/use-error criteria are found in the discussion guide Appendix 6 and section 4.1.1

During the simulated use participants are expected to undertake all steps as described in the IFU to perform a self-test using the LFD test kit.

This task begins with all the study components in their unopened form on the table and ends with the participant indicating that they have done everything they would do at home to perform the test.

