Use step 13 Gently squeeze the extraction tube to place 2 drops of liquid onto the specimen well on the test strip.	Participant tips the extraction tube to place 2 drops of liquid onto the test strip sample well.
Use step 14 Place the test strip on a flat and level surface Check the time or set a timer if you have one. Wait 30 minutes to read your result.	Participant places test strip on a flat surface Participant checks the time or sets timer for 30 minutes and leaves the test strip without touching it. After 30 minutes the participant reads the result.

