4.5 Simulated use caregivers of paediatrics and dependents

Participants will be asked to open the pack and to follow the steps of use presented to them to perform the test on their child/ dependent.

The simulated use steps to be observed are as follows in table 8:

Table 8 - Use	Steps for	adult testing	a child	or dependent

Use Step	Acceptance criteria
Repeat Use Steps 1 through 7 as per Section 4.4.1 (table 7) of this protocol, then proceed with Use Steps 8 and 9 below.	As per section 4.4.1 (table 7)
Use step 8 (child/dependant) Ask the child to open their mouth wide, then rub the fabric tip of the swab over both tonsils (or where they would have been). Do this with firm contact 4 times on each side. Carefully remove the swab. If you cannot swab the tonsils, you can swab both nostrils.	Participant rubs the fabric tip of the swab over both tonsils with firm contact 4 times on each side, without touching any part of the child/ dependent's mouth at this stage (not touching tongue, teeth, cheeks, gums etc). Participant removes the swab from the child/dependent's throat without touching any part of their mouth at this stage (not touching tongue, teeth, cheeks, gums etc)
Use Step 9 (child/dependent) Put the fabric tip of the same swab gently into one of their	Participant puts the fabric tip of the same swab gently into one of their nostrils Participant rolls the swab firmly
nostrils until you feel some resistance. Roll the swab firmly around the inside of the nostril, making 10 complete circles and slowly remove it. If you could not swab	around the inside of the nostril, making 10 complete circles and slowly removes it.
their throat repeat in their other nostril.	If the user could not swab the throat, they repeat in the other nostril.
Repeat Use Steps 10 through 14 , as per Section 4.4.1 (table 7) of this protocol.	As per section 4.4.1 (table 7)

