4.11 Analyses

After all sessions are completed, the collected data will be analysed to determine if the task performance was a success, use error, close call, or use difficulty, as per the criteria defined in Table 10. Root cause analysis will be conducted on all tasks where use errors, close calls, and use difficulties were present. This analysis will draw upon study video data, participant responses from post-task interviews, and expert review of the use problem.

Outcome	Definition	Root Cause Investigation Required?	Method of Scoring Data
Success	Participant performs the task correctly on the initial attempt without assistance	No	Success Close Call Use Error N/A

Table	10 -	Scoring	definitions
-------	------	---------	-------------

Outcome	Definition	Root Cause Investigation Required?	Method of Scoring Data
Close Call	 Any instance in which a participant makes a use error e.g. by attempting to undertake an action without accurate reference to the IFU, but then retries resulting in a successful completion of a user step. This outcome also considers: The user verbally expresses frustration or facial expressions and body postures indicate frustration when using the device; The user re-reads the same section of the IFU during a task, in an attempt to comprehend a sequence of steps use The user is able to accomplish a task or step, but experiences frustration or discomfort in the process of doing so. 	Yes	Success Close Call Use Error N/A
Use Error	 Any action or lack of action while using the packaging that leads to a different result than that intended by the manufacturer or expected by the user, including: A participant's inability to complete a task; A deviation from the IFU that leads to a device response that is different than intended or expected by the participant; An instance where the participant requires assistance from study personnel to advance through tasks. The following will not be considered use errors: A malfunction of the packaging that causes an unexpected result. 	Yes	Success Close Call Use Error N/A

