6.3.1 LFD TEST ADULT OR ADOLESCENT SELF TEST

Use Step/Acceptance criteria	Use Error	Use Difficulty	Close Call	Pass	Comments
Use Step 2					
Pour all of the fluid from the sachet into the extraction tube.					
Use Step 3 Place the filled tube in a cup or container to avoid spilling it while you use the swab					
Use Step 4 Check the swab in the sealed wrapper in front of you					
Use step 5 Gently blow your nose into a tissue.					
Use step 6 Wash and dry your hands again (or use sanitiser if this is available).					
Use Step 7 Open the swab package and gently take out the swab.					
Take your swab sample					
Use step 8 Holding the swab between your fingers, open your mouth wide and rub the fabric tip of the swab over both tonsils (or where they would have been). Do this with firm contact 4 times on each side (use a mirror to help you do this). Carefully remove the swab from the back of your throat.					

Use Step/Acceptance criteria	Use Error	Use Difficulty	Close Call	Pass	Comments
Use step 9					
Put the same swab gently into one nostril until you feel a slight resistance (about 2.5cm up your nose).					
Roll the swab firmly around the inside of the nostril, making 10 complete circles.					
Process the swab sample					
Use step 10					
Remove the extraction tube from the cup and place the fabric tip of the swab into the extraction tube so it is in the fluid.					
Press the tip against the edge of the extraction tube with force, while rotating it around the tube for 15 seconds.					
Use step 11					
Pinch the tube as you remove the swab to make sure that all the fluid is removed from the soft tip of the swab.					
Place the swab in the plastic waste bag provided.					
Use step 12					
Press the nozzle cap tightly on to the extraction tube to avoid any leaks					
Use step 13					
Gently squeeze the extraction tube to place 2 drops of liquid onto the specimen well on the test strip.					

Use Step/Acceptance criteria	Use Error	Use Difficulty	Close Call	Pass	Comments
Use step 14 Place the test strip on a flat and level surface Check the time or set a timer if you have one. Wait 30 minutes to read your result.					

START TIMER (30 minutes)

NOTE TO MODERATOR: AFTER STEP 14 ASK THE PARTICIPANT HOW LONG THEY SHOULD WAIT TO READ THE RESULTS

Wait full 30 minutes before reading results. A positive result can appear at any time after 20 minutes, however you must wait for a full 30 minutes to record a negative result as the test line may take longer to appear.

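### Step 14 counts reading the result after 30 minutes as observed behaviour, but the discussion guide times and announces that reading, and the scored interpretation follows questions on how to read a strip

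*Protocol*

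**What the plan says.** Two parts of the protocol deal with the reading of the result.

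**Acceptance criteria.** Table 7 in 4.4.1 gives step 14 four elements: the strip is placed on a flat surface; "Participant checks the time or sets timer for 30 minutes and leaves the test strip without touching it", which holds two elements; and "After 30 minutes the participant reads the result". Table 8 in 4.5 applies the same criteria to caregivers: "Repeat Use Steps 10 through 14 , as per Section 4.4.1 (table 7) of this protocol". For self-testers, 4.4 states that "the moderator will not interact with the participant during this task and will not offer help to the participant", and that the task "ends with the participant indicating that they have done everything they would do at home to perform the test". Table 10 in 4.11 defines Success as "Participant performs the task correctly on the initial attempt without assistance".

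**Discussion guide.** Both the self-test and the caregiver section carry this instruction: "NOTE TO MODERATOR: AFTER STEP 14 ASK THE PARTICIPANT HOW LONG THEY SHOULD WAIT TO READ THE RESULTS". Both also start a 30-minute timer. The note that the moderator keeps the time stands only in the self-test section. The wait is used for 6.5 (experience and root cause) and 6.6 (16 knowledge questions, with participants told to use the instructions). When the timer rings, 6.7 has the moderator say "We have now reached the time to read your test results. Can you now tell me what the result is". The answer is scored as success or use error on interpretation alone.

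**The concern.** A criterion for unaided behaviour needs a period in which the participant could fail it. Here the participant is kept in conversation throughout the wait and is then told that the time has come. Someone who would have forgotten the strip at home, or come back too late, looks the same as someone who would have read it on time.

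The second issue is order. Shortly before interpreting their own strip, participants answer Q9 and Q10 on reading time and Q11-Q13 on a positive, an invalid and a negative strip. Using the instructions is normal at home. Being taken through all three result types by an interviewer just before reading is not.

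The stated objective is to validate safe and effective use, and the instructions themselves stress the full wait. If the prompted reading were credited to step 14, the report would attribute to users a reading time that the script supplied. If 6.7 were presented as uncued, it could flatter the instructions.

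**Working it through.** The plan gives no statistical figure on this point, so there is none to reproduce. The check sets the criterion beside the script and counts what is affected.

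**1. Order of events in the guide.** Step 14 → question on waiting time → 30-minute timer → 6.5 → 6.6, including Q9-Q13 → timer rings → moderator announces → scored reading in 6.7.

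**2. Elements of step 14 against that order.**

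| Element (Table 7) | Observable unaided? |
|---|---|
| Strip on a flat surface | Yes, before any prompt |
| Time checked or timer set | Yes, before any prompt |
| Strip left untouched | Yes, on camera during the wait |
| Result read after 30 minutes | No; a late or forgotten reading is ruled out by the announcement |

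So 4 − 1 = 3 elements stay observable. A spontaneous early reading also remains visible.

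**3. Testers affected.** Self-testers: 15 adolescents + 15 adults = 30. Caregivers, through Table 8: 15 + 15 = 30. Total 60, because 6.5 to 6.7 are common to both branches.

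**4. Cueing before 6.7.** Q9-Q10 (timing) + Q11-Q13 (interpretation) = 2 + 3 = 5 of 16 questions, covering 3 of 3 result types. All 60 testers are asked under guide 6.6. If 4.6 is followed, which confines the questions to the adult participant, 60 − 15 adolescents = 45 are asked. The question after step 14 duplicates Q9.

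**5. Time.** Assumption, not in the protocol: 30 to 60 seconds per question. The guide gives 10 minutes for 6.5.

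- Wait filled now: 10 + 16 × (0.5 to 1) = 18 to 26 of 30 minutes; idle 4 to 12.
- Wait filled with Q9-Q13 moved: 10 + 11 × (0.5 to 1) = 15.5 to 21 of 30 minutes; idle 9 to 14.5.
- Time moved to after the reading: 5 × (0.5 to 1) = 2.5 to 5 minutes per session; × 60 = 150 to 300 minutes, or 2.5 to 5 hours in all.

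**6. Could an unaided reading be restored within the schedule?** Table 6 allots 30 minutes to the whole simulated use, and 30 − 30 = 0 is left for preparation and steps 1-13. The guide allots 40 minutes to simulated use and root cause together, leaving 40 − 30 = 10. Neither is comfortable, so the wait in practice has to overlap the interview.

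**The case against.** The best defence is that nothing in the protocol says the prompted reading will be counted towards step 14. Item 6.7 is separate and scored on interpretation only, and reading time has its own knowledge questions. That stands as far as it goes: the harm from crediting the reading to step 14 is conditional. It does not rescue the clause, which is listed as an acceptance criterion and has no unaided observation behind it.

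Four stronger readings are tempting, and the document does not support them.

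- A reader might infer that the script breaks the no-interaction rule of 4.4 for all 30 self-testers. The task ends when the participant signals completion, and the guide asks for that signal before the questions begin. The conflict arises only for self-testers who have not signalled before the wait, and their number is unknown.
- A reader might infer that the announcement is the only cue to read. The participant's own time check or timer is a step 14 element, and a timer is listed equipment in 3.11.
- A reader might treat every early reading as a use error. The guide says a positive line can appear from 20 minutes and requires the full 30 only for a negative.
- A reader might infer that a reading opened by the moderator cannot be Success under Table 10. It fits that definition poorly, but the assistance named under Use Error is help needed to get through tasks, and a scripted opening line is not clearly that.

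On cueing, no feedback on Q9-Q13 is scripted, and the instructions have their own section on results. Both points limit the likely effect; neither removes the order problem. It is also fair to say that asking Q11-Q13 after 6.7 lets one real strip reading precede them. That cue is small, because the answer is not confirmed and the questions are open-book anyway.

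**Conclusion.** The point holds, as something that should be corrected. One of the four elements of step 14 cannot be scored as unaided behaviour, because a late or forgotten reading is unobservable in 60 of 60 testers. The other three elements and a spontaneous early reading remain observable. Separately, the only scored reading of the participant's own strip follows five questions on timing and interpretation, so it may overstate uncued interpretation.

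The size of that second effect is unknown; the document gives no error rate and none is assumed here. The conclusion rests on the guide being followed as written. Later analysis cannot repair it, since the behaviour would never have been observed.

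**What to change.** 1. Delete the reading clause from step 14 in Table 7. Score the step on flat surface, time check or timer, and strip left untouched. Log any spontaneous early reading, and score it as a use error only if a negative result is recorded before 30 minutes.
2. Drop the waiting-time question after step 14 in both branches of the guide. Ask Q9-Q13 after the 6.7 reading, and fill the wait with 6.5, Q1-Q8 and Q14-Q16.
3. Report reading time as knowledge-only, from Q9 and Q10 asked of all 60 testers including adolescents, as guide 6.6 allows; 4.6 should be brought into line. Report 6.7 as a prompted reading.

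Cost: a few edits to the text, about 2.5 to 5 minutes per session moved to after the reading, more idle time during the wait (9 to 14.5 instead of 4 to 12 minutes, on the same assumption), and the small cue to Q11-Q13. The study would make no claim about unaided reading time, which it cannot support as scripted in any case.

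A separate minor alignment: the caregiver row for step 14 in the guide makes placement of the strip optional, whereas Table 7 requires a flat surface.

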6.8 Closing session (5 mins)

- 3. Considering the test that you have performed today what kind of support service do you prefer to use?
 - 1. Direct face to face HCP/pharmacy support
 - 2.Telephone support
 - 3.Connected solutions e.g Apps

That is all I would like to discuss today.

Is there anything that you would like to ask me about what you have seen today or to mention something that is important to you that I haven't asked about?

THANK PARTICIPANT.

REMIND PARTICIPANT TO PLACE THE WEBCAM IN THE PRE PAID ENVELOP AND RING THE NUMBER FOR COLLECTION

ambridge Office obal Innovation and Technology Centre [name]

consulting.com

is report has been prepared by PA onsulting Group on the basis of ormation supplied by the client, third rties (if appropriate) and that which is ailable in the public domain. No oresentation or warranty is given as the achievability or reasonableness future projections or the assumptions derlying them, targets, valuations, inions, prospects or returns, if any, nich have not been independently rified. Except where otherwise dicated, the report speaks as at the te indicated within the report.

l rights reserved PA Knowledge Limited 2019

is report is confidential to the organisation med herein and may not be reproduced, ored in a retrieval system, or transmitted in y form or by any means, electronic, echanical or otherwise, without the prior itten permission of PA Consulting Group. In e event that you receive this document in ror, you should return it to PA Consulting oup, Global Innovation and Technology entre, [name]. PA Consulting Group accepts no

About PA.

We believe in the power of ingenuity to build a positive human future in a technology-driven world.

As strategies, technologies and innovation collide, we create opportunity from complexity.

Our diverse teams of experts combine innovative thinking and breakthrough technologies to progress further, faster. Our clients adapt and transform, and together we achieve enduring results.

An innovation and transformation consultancy, we are over 2,800 specialists in consumer, defence and security, energy and utilities, financial services, government, healthcare, life sciences, manufacturing, and transport, travel and logistics.

We operate globally from offices across the Americas, Europe, the Nordics and the Gulf.
